2.4.3.2 Compliance

A given administration of IMP will be considered "noncompliant" if the patient did not take the planned dose of treatment as required by the protocol.

Percentage of compliance for a patient will be defined as $100 \times$ (the number of administrations the patient was compliant divided by the total number of administrations the patient was to take during the treatment period).

Above-planned dosing percentage for a patient will be defined as the number of administrations that the patient took a higher dose than planned divided by the total number of administrations that the patient was planned to take during the treatment epoch.

Under-planned dosing percentage for a patient will be defined as the number of administrations that the patient took a lower dose than planned divided by the total number of administrations that the patient was planned to take during the treatment epoch.

Note: Percentage of compliance + above-planned dosing percentage + under-planned dosing percentage will be lower than or equal to 100%, depending upon the definition of compliance (for instance, the required quantity may be administered, but too rapidly, so that the administration will not be counted as compliant or above-planned dose or under-planned dose).

Treatment compliance will be summarized by categories (eg, >80% compliant, >60 - 80% compliant, >40-60% compliant, <40% compliant). The percentage of patients with compliance <80% will be summarized.

In addition, the number and percentage of patients with at least 1 above-planned dosing administration will be given, as well as the number and percentage of patients with 0, >0 - 20%, and >20% under-planned dosing administrations. In addition, overall compliance will be summarized descriptively (N, mean, SD, median, minimum, and maximum).

2.4.4 Analyses of efficacy endpoints

Not applicable

2.4.5 Analyses of safety data

The primary and secondary analyses are safety related. All safety analysis will be performed on the safety population.

Statistical Analysis Plan
LPS15023 - Dupilumab

15-Mar-2021
Version number: 2.0

Treatment-emergent AE is defined as any AE with onset on or after the first dose of dupilumab up to the last dose of dupilumab plus 14 days for completers, or plus 84 days for prematurely discontinued subjects.

Primary endpoint:

- Incidence rates, defined as the percentage of patients reporting any treatment-emergent adverse events (TEAEs), and event rates, defined as the number of TEAE events per 100 person-years.

Secondary endpoints:

- Incidence rates and event rates per 100 person-years for AESIs over the study.
- Incidence rates for SAEs/death over the study.
- Incidence rates for AEs leading to study discontinuation over the study.

2.4.5.1 Analyses of adverse events

Analysis of Primary Safety Endpoint

Incidence rates of TEAEs with corresponding 95% CI (by the Clopper-Pearson method) will be calculated as follows:

- Incidence Rate (IR) = number patients with one or more TEAEs / number of subjects at risk (i.e. safety population) × 100

Event rates per 100 person-years of TEAEs with corresponding 95% CI (two-sided exact Poisson CIs) will be calculated. All events reported during the study follow-up period will be counted, regardless of whether they are reported in the same subject (i.e., multiple events per subjects), or different subjects. The person-years at follow-up will be calculated using the standard on-treatment duration formula: (the date of last IMP – date of first dose of IMP + 14 days)/365.25. Note that date of first dose of IMP, is in regards to first dose of this study, not first dose of the parent study. Event rate per person-years will be calculated as follows:

- Event rate (ER) = number of TEAEs / number of person-years at follow up

Analysis of Secondary Safety Endpoints

Incidence rates with corresponding 95% CI (Clopper-Pearson method) and event rates with corresponding 95% CI (exact Poisson method) will be presented for AESIs, described in [section 2.1.4.1](#), using the same methodology described above.

Incidence rates with corresponding 95% CI (Clopper-Pearson method) will be presented for SAEs/death over the study.

Incidence rates with corresponding 95% CI (Clopper-Pearson method) will be presented for AEs leading to study discontinuation over the study.

Generalities

The primary focus of adverse event reporting will be on treatment-emergent adverse events.

Statistical Analysis Plan
LPS15023 - Dupilumab

15-Mar-2021
Version number: 2.0

If an adverse event date/time of onset (occurrence, worsening, or becoming serious) is incomplete, an imputation algorithm will be used to classify the adverse event as pretreatment, treatment-emergent, or posttreatment. The algorithm for imputing date/time of onset will be conservative and will classify an adverse event as treatment emergent unless there is definitive information to determine it is pretreatment or posttreatment. Details on classification of adverse events with missing or partial onset dates are provided in [Section 2.5.3](#).

Adverse event incidence tables will present by SOC, HLTG, and PT, sorted in alphabetical order, the number (n) and percentage (%) of patients experiencing an adverse event. Multiple occurrences of the same event in the same patient will be counted only once in the tables within a treatment phase. The denominator for computation of percentages is the safety population.

Analysis of all treatment-emergent adverse events

The following treatment-emergent adverse event summaries will be generated for the safety population.

- Overview of treatment-emergent adverse events, summarizing number (%) of patients with any
 - Treatment-emergent adverse event
 - Treatment-emergent AESIs
 - Serious treatment-emergent adverse event
 - Treatment-emergent adverse event leading to death
 - Treatment-emergent adverse event leading to permanent treatment discontinuation
- All treatment-emergent adverse event by primary SOC, HLTG, and PT, showing number (%) of patients with at least 1 treatment-emergent adverse event sorted by the SOC internationally agreed order. The other levels (HLTG, PT) will be presented in alphabetical order

Analysis of all treatment emergent serious adverse event(s)

- All SAEs by primary SOC, HLTG, and PT, showing number (%) of patients with at least 1 treatment-emergent adverse event sorted by the SOC internationally agreed order. The other levels (HLTG, PT) will be presented in alphabetical order

Analysis of all treatment-emergent adverse event(s) leading to treatment discontinuation

- All TEAEs leading to treatment discontinuation by primary SOC, HLTG, and PT, showing number (%) of patients with at least 1 treatment-emergent adverse event sorted by the SOC internationally agreed order. The other levels (HLTG, PT) will be presented in alphabetical order

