10.4.2 General guidelines for reporting adverse events

- All AEs, regardless of seriousness or relationship to IMP/NIMP, spanning from the signature of the ICF until the end of the study as defined by the protocol for that patient, are to be recorded on the corresponding screen(s) of the eCRF.
- Whenever possible, diagnosis or single syndrome should be reported instead of symptoms. The Investigator should specify the date of onset, intensity, action taken with respect to IMP, corrective treatment/therapy given, additional investigations performed, outcome, and his/her opinion as to whether there is a reasonable possibility that the AE was caused by the IMP or by the study procedure(s).
- The Investigator should take appropriate measures to follow all AEs until clinical recovery is complete and laboratory results have returned to normal, or until progression has been stabilized, or until death, in order to ensure the safety of the patients. This may imply that observations will continue beyond the last planned visit per protocol, and that additional investigations may be requested by the monitoring team up to as noticed by the Sponsor.
- Patients who experience an ongoing SAE or an AESI with immediate notification, at the pre specified study end-date (EOT/EOS Visit), should be followed until resolution, stabilization, or death and related data will be collected.
- When treatment is prematurely and permanently discontinued, the patient's observations will continue until the end of the study as defined by the protocol for that patient.
- The following laboratory abnormalities are considered clinically significant and will be recorded as AEs:
 - Symptomatic and/or
 - Requiring either corrective treatment or consultation, and/or
 - Leading to IMP discontinuation or modification of dosing, and/or
 - Fulfilling a seriousness criterion, and/or
 - Defined as an AESI.

Instructions for AE reporting are summarized in [Table 1](#) in [Section 10.4.5](#).

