11.4.3.1.1 Treatment-emergent adverse events

Incidence of TEAE and the number of TEAEs per 100 patient-years (total number of events adjusted for the total duration of exposure) will be presented by system organ class (SOC), high level group term (HLGT), and preferred term (PT) sorted in alphabetical order, the number and percentage (%) of patients experiencing a TEAE.

In the derivation of incidence of AEs, multiple occurrences of the same event in the same patient will be counted only once in the tables. The denominator will be based on the total number of patients in the safety population.

The proportion of patients with at least one TEAE, serious TEAE, and TEAE leading to discontinuation of the study will be tabulated. In addition TEAEs will be described according to maximum intensity and relationship to the study drug.

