 - Follow-up of the pregnancy in a female participant or in a female partner of a male participant is mandatory until the outcome has been determined.
- Symptomatic overdose (serious or nonserious) with the IMP/NIMP.
 - An overdose (accidental or intentional) with the IMP/NIMP is an event suspected by the Investigator or spontaneously notified by the patient and defined as at least twice the planned dose during an interval of less than 11 days. The circumstances (i.e. accidental or intentional) should be clearly specified in the verbatim and symptoms, if any, entered on separate AE forms.
 - Of note, asymptomatic overdose has to be reported as a standard AE.

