If the assessment of the relationship to IMP is missing, then the relationship to IMP is assumed to be possibly related in summary tables, but no imputation will be presented in the listings.

Handling of missing severity of adverse events

If the severity is missing for 1 of the treatment-emergent occurrences of an adverse event, the maximal severity on the remaining occurrences will be considered. If the severity is missing for all the occurrences, a “missing” category will be added in the summary table.

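### The exact Poisson 95% CIs on the TEAE and AESI event rates ignore dependence between events in the same patient, so they may be too narrow by an amount the documents do not let us determine

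*SAP*

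**What the plan says.** SAP 2.4.5 makes the event rate the second part of the primary endpoint: "event rates, defined as the number of TEAE events per 100 person-years". SAP 2.4.5.1 then gives the interval: "Event rates per 100 person-years of TEAEs with corresponding 95% CI (two-sided exact Poisson CIs) will be calculated". The numerator rule follows directly: "All events reported during the study follow-up period will be counted, regardless of whether they are reported in the same subject". The denominator is summed on-treatment person-years. The secondary analysis applies the same methodology to AESI event rates.

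The protocol (11.4.3.1.1) asks for "the number of TEAEs per 100 patient-years (total number of events adjusted for the total duration of exposure") and specifies no interval, so the CI is an addition made in the SAP.

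Three other places bear on within-patient dependence:

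- SAP 2.4.5.1, on the incidence tables: "Multiple occurrences of the same event in the same patient will be counted only once in the tables within a treatment phase". This governs the n (%) tables, not the event rate.
- SAP 2.5.2 foresees several occurrences of one event in a patient ("If the severity is missing for 1 of the treatment-emergent occurrences of an adverse event"). SAP 2.1.4.1, on overdose, says that the circumstances "should be clearly specified in the verbatim and symptoms, if any, entered on separate AE forms".
- Protocol 10.4.2 works in the other direction: "Whenever possible, diagnosis or single syndrome should be reported instead of symptoms".

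Neither document provides a robust variance, a dispersion parameter, a bootstrap or a sensitivity analysis for this interval. SAP 2.5.6 (statistical technical issues) is marked as not applicable.

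**The concern.** An exact Poisson interval depends only on the total count. It gives 1,000 events from 100 patients the same precision as 1,000 events from 1,000 patients. That is justified only if events are independent. Two departures matter:

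- **Episodes.** If one clinical episode produces several AE records, the variance of the total exceeds its mean, whatever population the CI is meant to describe and however rare the events are.
- **Different patient rates.** If some patients are more prone to events than others, the total varies more than Poisson when patients are regarded as a sample from a wider population.

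The study is for estimation only, so this interval is the only stated measure of uncertainty for the event-rate half of the primary endpoint. At stake is a reported precision that the data may not support.

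**Working it through.** **No figure to reproduce.** The documents give no expected TEAE rate, event count, interval width or dispersion. From the documents: about 750 patients (SAP 1.3) and at most 144 weeks of treatment (SAP 1.1), that is 144 × 7 / 365.25 = 2.76 years. Assumed: TEAE rates r of 0.5 to 3 per person-year (PY); AESI rates of 2 to 5 per 100 PY; follow-up T uniform on 0.25–2.76 years (long) or 0.25–1.0 year (short); gamma-distributed patient rates with relative variance k; episode size c, either geometric or 1 + Poisson.

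**Intervals compared.** For x events, exact Poisson runs from χ²(0.025; 2x)/2 to χ²(0.975; 2x + 2)/2, divided by person-years. The robust interval is on the log rate, with SE = √[n/(n−1) × Σ(events − rate × PY)²] / total events, summed over patients.

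**Variance relative to Poisson (φ); coverage ≈ 2Φ(1.96/√φ) − 1.**

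- Episodes only: φ = E[c²]/E[c]. Neither r nor T appears. For geometric c with mean μ, φ = 2μ − 1: 1.5 at μ = 1.25 (coverage 89.0%), 2 at 1.5 (83.4%), 3 at 2 (74.2%), 5 at 3 (61.9%).
- Rate differences only, patients as a random sample: φ = 1 + k·r·E[T²]/E[T]. For long follow-up E[T²]/E[T] = [(0.25² + 0.25 × 2.76 + 2.76²)/3] / 1.505 = 1.854; for short it is 0.70. At r = 1, long: k = 0.25 gives φ = 1.46, k = 1 gives 2.85.

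**Simulation, overall TEAE rate** (4,000 trials of 750 patients per cell, Monte Carlo SE at most 0.8 points):

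| Scenario | Exact Poisson coverage |
|---|---|
| No clustering, equal rates | 95% |
| Episodes, mean 1.1 / 1.25 / 1.5 / 2 / 3 (any r, either follow-up, both shapes) | 92–94 / 89–91 / 82–87 / 73–80 / 60–71% |
| k = 0.25, r = 0.5 / 1 / 2 / 3, short | 95 / 93 / 92 / 89% |
| k = 0.25, same rates, long | 93 / 90 / 84 / 79% |
| k = 1, same rates, short | 92 / 85 / 80 / 74% |
| k = 1, same rates, long | 85 / 77 / 64 / 56% |
| Enrolled patients' rates held fixed, no clustering | 94–96% |
| Fixed rates (k = 1, r = 1.5) with episodes of mean 1.25 / 1.5 / 3 | 89 / 83–84 / 60–62% |

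Repeat runs of the cell r = 1, k = 1, long follow-up gave 75 to 77%. The robust CI covers 94–96% in the episodes-only and random-patient cells. At r = 1 with long follow-up the mean widths per 100 PY are 11.8 (Poisson) against 14.1 (robust) at k = 0.25, and 11.8 against 19.7 at k = 1.

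**Simulation, AESI-like rates.** Expected counts run from 750 × 0.625 × 0.02 ≈ 9 to 750 × 1.505 × 0.05 ≈ 56.

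- Rate differences only, k up to 2: Poisson coverage 94–97%, so there is essentially no harm.
- Geometric episodes: Poisson coverage about 90–92% (mean 1.25), 85–87% (1.5), 75–78% (2) and 63–67% (3). The robust CI covers about 84–95% and does better than Poisson in every clustered cell. Its worst case, about 9 expected events and mean 3 per episode, is 84–85%, against 66–67% for Poisson.

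**The case against.** **The enrolled patients may be the population of interest.** The objective is descriptive, all qualifying TRAVERSE completers are offered enrolment, and there is no comparator. If their rates are taken as fixed, a sum of independent Poisson counts is still Poisson, and differing rates do no harm. This stands, but the SAP does not state that reading, and it does not remove the episode mechanism.

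**Evidence for clustering is thin.** The provision for several occurrences shows repeat events, and repeats alone leave coverage at 95%. The separate-forms instruction concerns overdose, which is a listed AESI when symptomatic. The instruction to report a diagnosis instead of symptoms reduces clustering. This also stands. A reader might infer that the documents show the interval to be materially too short; they do not. They show only that nothing guards against it.

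**Counting all events is correct.** A reader might infer that the numerator rule is the error, or that the once-per-patient rule should be carried over to the event rate. Neither follows: an event rate needs all events, and the protocol defines it that way. Only the variance is in question.

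**Sparse AESI counts suit an exact method.** This holds against rate differences. It does not hold against episodes, because that variance ratio does not depend on the rate.

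**Conclusion.** The point holds, with minor severity. The exact Poisson interval for TEAE and AESI event rates is too narrow if events cluster in episodes. For the overall TEAE rate it is also too narrow if patients' rates differ and the CI is read beyond those enrolled; for sparse AESI rates that second mechanism is negligible at k up to 2.

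The size is unknown. Under the assumptions above it runs from nothing to severe, and the lowest coverages need strong heterogeneity with high rates and long follow-up, or large episodes. A reader might take the low coverage figures as a prediction for this trial, or conclude that the primary analysis is invalid. The documents support neither: they give no rate, dispersion or clustering, the point estimates and Clopper-Pearson CIs are unaffected, and no test or decision rule uses the interval.

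**What to change.** Keep the estimator, total events over total person-years, and change only the interval in SAP 2.4.5.1:

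- **Overall TEAE event rate:** replace the exact Poisson CI with a patient-level robust (sandwich) 95% CI on the log rate, from a Poisson model with log person-years as offset and variance clustered by patient.
- **AESI event rates:** report the same robust CI beside the exact Poisson CI. Add a note that the Poisson CI assumes independent events and that the robust CI can itself under-cover at very small counts. With no events, report the exact Poisson CI alone.

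The cost is SAP wording and a few lines of code, with no new data. The TEAE interval will be wider if there is dependence. With neither clustering nor heterogeneity its width is 0.98–1.00 times the Poisson width. If the enrolled patients' rates are treated as fixed and events do not cluster, the robust CI is conservative (95–100% coverage). A sentence in the SAP stating which population the CI describes would make that trade-off explicit, but would not by itself deal with episodes.

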10.1.5 End-of-study Visit

Patients who prematurely and/or permanently discontinue treatment will be scheduled for the EOT Visit, and the EOS Visit will be scheduled for 12 weeks later for follow-up on AEs.

The following procedure will be performed during this visit:

- Inquire for any AEs. In case of any such occurrences, AEs should be recorded and reported.

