11.3.2 Safety population

The primary analysis population is the safety population, which is defined as all patients who have actually received at least one dose or part of a dose of dupilumab during this study.

The treatment-emergent period is defined as the time from the first dose of dupilumab during this study up to the EOT/EOS (Visit 13).

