11.4.1.1 Extent of investigational medicinal product exposure

Duration of exposure to IMP is defined as: last dose date – first dose date of dupilumab + dose interval, regardless of unplanned intermittent discontinuations. Duration of exposure will be summarized using descriptive statistics such as mean, standard deviation (SD), median, minimum, and maximum.

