2.3.2 Safety population

The primary analysis population is the safety population, defined as all patients who have received at least one dose or part of a dose of dupilumab during this study.

Statistical Analysis Plan
LPS15023 - Dupilumab

15-Mar-2021
Version number: 2.0

The treatment-emergent period is defined as the time from the first dose of dupilumab up to the last dose of dupilumab plus 2 weeks for completers, or plus 12 weeks for prematurely discontinued subjects.

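### Event rates count adverse events to 84 days after last dose in premature discontinuers but stop everyone's person-time at 14 days, so the rates are biased upward

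*SAP*

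**What the plan says.** **Event window.** SAP 2.3.2 (Safety population) runs the treatment-emergent period from first dose "up to the last dose of dupilumab plus 2 weeks for completers, or plus 12 weeks for prematurely discontinued subjects". SAP 2.4.5 repeats the rule in days: "up to the last dose of dupilumab plus 14 days for completers, or plus 84 days for prematurely discontinued subjects".

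**Rate.** SAP 2.4.5.1 defines "Event rate (ER) = number of TEAEs / number of person-years at follow up". The person-years come from the "on-treatment duration formula: (the date of last IMP – date of first dose of IMP + 14 days)/365.25", with no separate rule for premature discontinuers. The same section counts repeat events and applies the same method to AESI event rates.

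**Protocol.** Section 11.4.3.1.1 describes the rate as "total number of events adjusted for the total duration of exposure", and section 11.4.1.1 defines exposure as "last dose date – first dose date of dupilumab + dose interval, regardless of unplanned intermittent discontinuations". The SAP denominator follows these two sections. The SAP event window differs from the protocol's: section 11.3.2 ends the treatment-emergent period at the EOT/EOS visit (Visit 13). SAP 1.5, which should record departures from the protocol's statistical section, lists none.

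**Follow-up.** For patients who stop early, protocol 10.1.5 says "the EOS Visit will be scheduled for 12 weeks later for follow-up on AEs".

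**The concern.** In completers, events and person-time both end 14 days after the last dose. In premature discontinuers, events run on to day 84 while person-time still ends at day 14. Days 15 to 84 are time in which events are actively sought and counted, yet nobody is credited as being at risk. No passage extends the denominator for these patients or limits the rate's numerator to day 14.

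The error has one direction. It grows with the share of premature discontinuers and with shorter average exposure. It does not shrink as the sample grows, and the exact Poisson interval does not reflect it. The study is single-arm and descriptive, so these rates are a main output, and no control arm carries the same distortion. Incidence percentages, including those for SAEs/death and for AEs leading to study discontinuation, have patients as their denominator and are unaffected.

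**Working it through.** The plan states no event rate, discontinuation rate or precision figure, so there is nothing of its own to reproduce.

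**Inputs from the documents:** event window of last dose + 14 or + 84 days (SAP 2.3.2, 2.4.5); person-time to last dose + 14 days (SAP 2.4.5.1); about 750 patients and at most 144 weeks of treatment (SAP 1.1).

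**Assumed inputs:** share *p* discontinuing prematurely, 5% to 30%; mean person-time *m* by the SAP formula, 0.75 to 2.5 years.

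**Gap per premature discontinuer:** 84 − 14 = 70 days; 70/365.25 = 0.1916 person-years (PY).

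**Cohort effect.** Let x = p × 0.1916 / m. Compared with the rate whose person-time runs to the end of the event window, the SAP rate is too high by x and its denominator too short by x/(1 + x). This comparison uses the same events in both rates, so it does not depend on how frequent events are in days 15 to 84.

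| p | m (years) | Rate too high by | Denominator short by | PY missing at N = 750 | Rate too high if half the gap is observed |
|---|---|---|---|---|---|
| 5% | 2.5 | 0.38% | 0.38% | 37.5 × 0.1916 = 7.2 | 0.19% |
| 15% | 1.5 | 1.92% | 1.88% | 112.5 × 0.1916 = 21.6 | 0.96% |
| 30% | 0.75 | 7.67% | 7.12% | 225 × 0.1916 = 43.1 | 3.83% |

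For each pair (p, m) the fourth-to-last figure, the rate excess, is a ceiling, because it assumes that every discontinuer is followed for all 70 days. The last column shows the effect if death or loss to follow-up leaves half of that time observed.

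**Middle case** (p = 15%, m = 1.5, assumed true rate 200 per 100 PY). SAP person-time is 750 × 1.5 = 1125.0 PY; aligned person-time is 1125.0 + 21.6 = 1146.6 PY. Expected events are 2.00 × 1146.6 = 2293.
- As written: 100 × 2293/1125.0 = 203.8 (exact Poisson 95% CI 195.6 to 212.3).
- Aligned: 100 × 2293/1146.6 = 200.0 (191.9 to 208.3).

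**Single patient.** With d days of SAP person-time, a discontinuer's own rate is multiplied by (d + 70)/d: 154/84 = 1.83 at 84 days and 238/168 = 1.42 at 168 days.

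**Comparison with a strict 14-day rate.** Here the excess is the number of events in days 15 to 84 relative to the number up to day 14. It is zero if no TEAE falls in days 15 to 84, and equals x if events occur at the on-treatment rate. Example: 20% discontinue, completers have 144 weeks and discontinuers 72. SAP person-time is 1862.8 PY and the gap is 150 × 0.1916 = 28.7 PY, an excess of 1.5%. It becomes 0.8% if the event rate in days 15 to 84 is half the on-treatment rate and 3.1% if it is double.

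**The case against.** The best counter-argument is that the protocol specifies events per unit of exposure, and the SAP openly uses an on-treatment duration. On that view the rate is a disclosed, exposure-adjusted quantity, and it is biased only if a time-at-risk rate was intended. It is true that the denominator is the protocol's. But the differential 14/84-day event window is the SAP's own, and nothing sets the two against each other. The SAP also calls its denominator follow-up time. The resulting rate is never below either consistent rate. It exceeds the 84-day rate whenever discontinuers are followed past day 14, and exceeds the 14-day rate whenever a TEAE falls in days 15 to 84.

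Three other points stand in part:

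- **Size.** The effect is probably small, and the percentages rest on assumptions. They illustrate rather than bound: 50% discontinuing with 48-week completers and 24-week discontinuers would give 13.9%. The route to short exposure that the documents name is market availability. If those patients count as completers, they have no gap.
- **Consequence.** There is no hypothesis test or decision threshold, and the error overstates harm, so it cannot hide a signal.
- **Follow-up.** Full observation to day 84 is not assured. The protocol synopsis and section 10.1.3 send discontinuers to one combined EOT/EOS visit, and section 10.3.5 lets patients decline it. The 70 days is therefore a ceiling, and aligned person-time has to be cut off at last contact.

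These points limit the severity. They do not make the two windows agree.

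**Conclusion.** The concern holds. The numerator and denominator of the primary and AESI event rates cover different time in premature discontinuers, and the rates are pushed upward. Under the assumed 5% to 30% discontinuation and mean person-time of 2.5 down to 0.75 years, the overstatement against the 84-day aligned rate is at most 0.4% to 7.7%, or 0.2% to 3.8% if only half the gap is observed. In the middle case the shift of 3.8 per 100 PY is less than half of the interval's half-width of about 8.3. Large factors arise only for patients who stop early. This should be fixed before analysis because the definition is internally inconsistent and cheap to correct. It does not threaten the study's descriptive conclusions.

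**What to change.** Use one window for both parts of the rate in SAP 2.4.5.1.

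- **Suggested primary:** keep the SAP 2.3.2 event window. End person-time at the earliest of last dose + 14 days (completers) or + 84 days (premature discontinuers), death, or last contact. Define last contact from recorded dates.
- **Suggested sensitivity analysis:** restrict events and person-time to last dose + 14 days for everyone, and tabulate events on days 15 to 84 separately.

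The reverse order is equally valid if stated in advance.

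Three smaller corrections belong in the same edit. None of them causes the overstatement.

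1. Write the rate as 100 × TEAEs / person-years, to match the stated scale.
2. State whether patients who stop at market availability are completers. The natural reading of SAP 1.4 is that they are, and this decides who gets the 84-day window.
3. Record in SAP 1.5 the change from the treatment-emergent period in protocol 11.3.2 and any change from the exposure denominator in protocol 11.4.3.1.1.

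The cost is SAP wording and one derived variable. No new data are needed, because the protocol already schedules an adverse-event follow-up visit 12 weeks after EOT for these patients. Event rates fall slightly under the suggested primary. Under the 14-day version, later events move to their own table.
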